2

3 4 5

6

12

13 14

15

16

17

18 19

20

21

22

23

24 25

26

31

37

41

46 47

Brooke Army Medical Center Institutional Review Board

HUMAN SUBJECTS RESEARCH PROTOCOL APPLICATION – Part B

1. PROTOCOL TITLE: Incorporation of Mindfulness Exercises to Reduce Anxiety and Pain during Urodynamic Testing: A Randomized Controlled Trial

2. ABSTRACT Urodynamic study (UDS) is a series of tests that evaluate bladder and urethral function. UDS is associated with pain and anxiety due to the invasive nature of the testing. Several interventions have been attempted to reduce the unpleasantness associated with UDS without success. A novel technique that has been shown to reduce chronic bladder pain is mindfulness. We want to study the changes in patient's perceptions of UDS after a mindfulness intervention.

3. OBJECTIVES/SPECIFIC AIMS/RESEARCH QUESTIONS.

The objective of the study is to investigate whether mindfulness techniques improve patient's perceptions of UDS testing.

- 1. Objective #1-To evaluate changes in anxiety symptoms during UDS testing.
 - Hypothesis: anxiety will improve during UDS testing with prior mindfulness intervention.
- 2. Objective#2- To evaluate changes in pain intensity during UDS testing.
- Hypothesis: pain will improve during UDS testing with prior mindfulness intervention

4. MILITARY RELEVANCE

Pain and anxiety that may be present in UDS impacts the emotional and physical distress experienced by active duty service members and beneficiaries who need testing. The emotional and physical distress can interfere with the accuracy of their diagnosis so that the proper treatment is not administered for their bothersome urinary issues. This may lead the patient to suffer and this may restrict them from vital training, military readiness, or important life events.

32 5. BACKGROUND AND SIGNIFICANCE

Urodynamic study (UDS) is a series of tests that evaluate the bladder and urethral function. UDS involves placing
 catheters that are into the bladder and rectum that can be uncomfortable. UDS is conducted by several people during
 testing and UDS may require an extended amount of time that can further add to the emotional and physical demands.
 Not surprisingly, UDS has been reported to be associated with anxiety, embarrassment, and pain^{1,2}.

Several previous techniques to improve patient's perceptions during UDS have been unsuccessful³⁻⁵. These interventions
 include lavender oil, music, and an educational video, and have not improved patients' experiences during UDS. Written
 patient educational material given before UDS testing has mixed results in the literature³⁻⁴.

42 Mindfulness based stress reduction is a technique that improves coping during stress events. Mindfulness has been 43 shown to reduce anxiety and pain in the chronic pain disorders of the bladder⁶. Mindfulness can enhance, "detached 44 observation" which can aid in reducing subjective negative evaluation of nociceptive stimuli⁷. It has been suggested that 45 mindful meditation enhances self-regulation which is beneficial during physically and emotionally taxing experiences⁷

48 6. RESEARCH DESIGN

A prospective randomized controlled pilot trial will be conducted from patients that undergo UDS testing. Eligible study subjects that are willing to participate will be accrued from the Urology clinic. Subjects will be consented by the Pl. Subjects will be randomized between standard clinic UDS or UDS with mindfulness exercises. Subjects will not be blinded to the intervention or control group, although the physician performing the UDS will be blinded to the allocation of treatment. A power calculation was performed and 30 subjects are required for this study. Assessment or methodology will be from questionnaires after UDS testing. All subjects will be evaluated with an anxiety questionnaire, urodynamic discomfort guestionnaire, and pain visual analog scale.

56

59 **7.** **RESEARCH PLAN** 60

61 7.1 Selection of Subjects

7.1.1. Subject Population. The target population includes all adult (DoD beneficiaries) and active duty patients over the age
 of 18 that are scheduled to have UDS testing. Pregnant women, children, basic trainees or other special populations will not
 be included.

67 **7.1.2. Source of Research Material**.

68

Source of Research Material	Clinical Purposes(Y/N)	Research Purposes (Y/N)
Anxiety Questionnaire	Ν	Υ
UDS Questionnaire	Ν	Y
Pain VAS	Ν	Y

69

70 7.1.3. Inclusion and Exclusion Criteria. Inclusion criterion includes adults (DoD beneficiaries and active duty patients
 71 over the age of 18-80) scheduled for UDS testing. Diagnosis to include urinary symptoms requiring urodynamic testing are
 72 stress urinary incontinence, Mixed urinary incontinence, Urgency urinary incontinence, overactive bladder, urinary
 73 retention, and lower urinary tract symptoms.

Exclusion criteria include age less than 18 years, pregnant-as verified by urine or blood sample, have an alteration in
 neurologic bladder function, or inability to provide informed consent. Condition that will be excluded include neurogenic
 bladder, Interstitial cystitis, chronic bladder pain, and inability to have urodynamics performed.

77 78

84

93

96

79 7.1.4. Description of the Recruitment and Prescreening Process. The PI will be present at UDS testing and, in the same
 80 setting, will identify potential study participants by reviewing their medical record. The PI will recruit potential study
 81 participants for enrollment into this study by discussing it with them and reviewing the attached consent. After completion of
 82 informed consent, subjects will be enrolled in the study. Subjects will register into the study and entered into randomization as
 83 described previously.

7.1.5. Subject Screening Procedures. Pregnancy testing for subjects will the possibility of becoming pregnant which is
 already routine testing before UDS testing. Patients who, based on medical record or clinic visit, lack capacity to provide
 informed consent will not be included in the study.

7.1.6. Consent Process. The PI will obtain the informed consent in a private clinic room on the day of the UDS testing. For
subjects who wish to participate in the study, informed consent will be obtained at the time of counselling by the PI. Subjects
who do not demonstrate the ability to understand or the willingness to sign the written consent document will be excluded from
study entry.

7.1.7. Compensation for participation. No compensation or payment to subjects will be made for participation in this
 study.

97 **7.2 Drugs, Dietary Supplements, Biologics, or Devices.**

- 98 99 **7.2.1 N/A**
- 100
- 101 7.2.2 N/A

7.3. Study Procedures/Research Interventions. Potential subjects will be invited to participate in this study by the PI, when 103 it is determined that a UDS evaluation is appropriate for their standard treatment. All subjects who agree to participate will be 104 randomized into either the control group or the intervention (mindfulness exercise) group. Randomization assignment will be 105 106 computer generated at a 1:1 ratio. On the day of their scheduled appointment subjects will present to the Urology Clinic at SAMMC. All subjects will be escorted to an exam room within the Urology Clinic, as per usual protocol, where they will be 107 108 consented to participate in the study. After consenting to participate, subjects will be asked to complete an initial self-report 109 assessment of state anxiety (see attached). Following completion of the initial state-anxiety assessment, subjects in the control group will be asked to sit alone quietly in the exam room with the lights on, uninterrupted, for 10 minutes. They will be 110 given no other instructions other than to wait in the exam room. Subjects in the intervention group will be lead through a 111 112 mindfulness exercise in which they will be asked to focus their attention on their breath (see attached script). This exercise will take approximately 10 minutes and will be led by a Clinical Psychologist. Mindfulness exercises facilitate a state of detached 113 observation of the subject's situation and reduce negative physical and emotional stimuli7. At the end of the 10 minutes 114 (control) or the completion of the mindfulness exercise (intervention), all subjects will complete a second state-anxiety 115 assessment. Routine UDS evaluation (one catheter in the rectum and one catheter in the bladder) will commence for all 116 subjects. Following completion of the UDS evaluation, subjects will complete a third and final assessment of state-anxiety in 117 which they will be asked to assess their level of anxiety when it was at its highest while undergoing the UDS evaluation. 118

- 119
- 120
- 121
- 122

Assessment	Visit / Follow Up (F/U) Interval		
Study Day /	1 week	Procedure	
period	before		
Informed		х	
Consent, discuss			
Plan, etc.			
Randomization		х	
Demographics,		х	
History &			
Physical			
Anxiety Questionnaire		х	
UDS Questionnaire		Х	
Pain VAS		Х	
Self-evaluation		Х	
Questionnaire			

- 123
- 124 7.3.1 Collection of Human Biological Specimens, N/A 125
- 126 7.3.1.1 Laboratory evaluations and special precautions. N/A 127

128 7.3.1.2 Specimen storage. N/A 129

130 7.3.2 Data Collection. A de-identified electronic database will be maintained by the PI and associate PIs on a CAC protected computer. Access to the database will be only by study investigators. Database will be password and firewall 131 protected. There will be no transmission of data or external databases. 132

133

135

- 134 7.3.3. Human Biological Specimens/Tissue/Data Banking. N/A
- Statistical Consideration 136

137 138 7.4 7.4.1 Sample Size Estimation. Based on a sample size calculation, to achieve an alpha of 0.05 with power of 80% 139 sample size should incorporate 25 subjects. After accounting for 15-20% drop out/withdrawal, a total of 30 patients should 140 be enrolled.

- 141
- 142

Estimate Required Sample Size	25
Estimate Participant Drop Out / Withdrawal	5
Total Enrollment Requirement	30
Enrollment at Each Site	
BAMC	30

148

143

7.4.2 Primary (i.e., primary outcome variables) and secondary endpoints. The primary outcome is a reduction in anxiety
 as measured by the anxiety survey. Secondary outcome is a reduction in physical distress as measured by the pain VAS and
 UDS survey. Secondary endpoints will include self-evaluation questionnaires to assess differences between both groups.

7.4.3 Data analysis. ANOVA will be used to compare the visual analog scale scores between groups. Paired t-test will be used to evaluate the anxiety difference. Chi-squared test will be used to compare self-evaluation categories between both groups.

153 7.7 Confidentiality. Questionnaires will be de-identified of PII. Data will be entered into the database within 24 hours of collection. Questionnaires will then be stored in a locked cabinet in the Urology Clinic, only accessible by [name]. 154 155 Electronic database will be stored on a CAC protected computer within a password protected folder. Only investigators in this 156 study will have access to the electronic database. Upon completion of the study, hard copy data will be archived and secured in a locked cabinet within a locked office. The signed informed consent documents will be retained for 3 years and the signed 157 HIPAA Authorizations will be maintained for 6 years after the date of completion, after which, the files will be destroyed in 158 HIPAA approved disposal container and electronic data will be destroyed through the Information Management Division (IMD) 159 as per SAMMC protocol. 160 161

162 **7.7.1 Certificate of Confidentiality.** Particularly sensitive information will not be collected.

164 8.0 RISKS/BENEFITS ASSESSMENT

8.1 Risks. Risks associated with participating in this study are minimal. There is a very slight risk for loss of
 confidentiality. This risk will be minimized by maintaining data on secure computers. There may be minimal risks to
 subjects of emotional unease by participating in mindfulness exercises.

170

173

175

163

165

8.2 Potential Benefits. Subjects may experience lower levels of anxiety, pain and/or discomfort after undergoing
 mindfulness exercises.

174 9.0 ADVERSE EVENTS, UNANTICIPATED PROBLEMS, AND DEVIATIONS

9.1 No adverse events are anticipated. If subjects are not comfortable with the UDS testing, we will stop testing as per standard clinic protocol.

9.2 Reporting Unanticipated Problems Involving Risks to Subjects or Others, Serious Adverse Events and Deaths to the Office of the IRB, BAMC.

181

All unanticipated problems involving risk to subjects or others, serious adverse events, and all subject deaths related to the study will be reported within 48 hours of the research team's knowledge of the event by [contact]), by e-mail ([contact]), by [contact]) or via letter addressed to Human Protections Administrator, Office of the Institutional Review Board, Brooke Army Medical Center, Attn: MCHE-CI,[name]. A complete written report will follow the initial notification within 10 working days.

190 9.3 Research Monitor. N/A

191

189

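### The primary outcome is an unnamed reduction in anxiety tested with a paired t-test, and no within-person reduction among the three assessments answers Objective 1

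*Combined protocol and SAP*

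**What the plan says.** Section 3 states Objective 1 as "To evaluate changes in anxiety symptoms during UDS testing", with the hypothesis that "anxiety will improve during UDS testing with prior mindfulness intervention".

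Section 7.3 describes three state-anxiety assessments:

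1. After consent, before the 10-minute period.
2. After the 10 minutes of sitting quietly or the mindfulness exercise, when "all subjects will complete a second state-anxiety" form, still before UDS.
3. After UDS, an assessment in "which they will be asked to assess their level of anxiety when it was at its highest while undergoing the UDS evaluation".

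Section 7.4.2 states: "The primary outcome is a reduction in anxiety", as measured by the anxiety survey. It gives no assessment, score or contrast. Section 7.4.3 states: "Paired t-test will be used to evaluate the anxiety difference". It does not say which two assessments are paired, or whether the test is run in each arm or over all subjects. No between-arm analysis of anxiety is specified.

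Section 6 says: "Assessment or methodology will be from questionnaires after UDS testing". Two of the three anxiety assessments in Section 7.3 come before UDS. The schedule table in Section 7.3 has a single mark for the anxiety questionnaire on the procedure day, so it does not settle the matter.

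**The concern.** A paired test of a reduction needs two measurements of the same quantity, and the second must describe the period that the objective is about. The three assessments offer no such pair. The plan could therefore declare success from a fall in anxiety in the exam room, with no evidence about UDS. It could also find no reduction, or an increase, although mindfulness helped, because the test and the peak question raise the third score in both arms.

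Because the contrast is not named, it could also be chosen after the data are seen. The reduction that is easiest to show is probably the pre-UDS one, which does not address Objective 1.

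**Working it through.** **The plan's own figure.** Section 7.4.1 gives 25 subjects (alpha 0.05, power 80%) and 30 after 15–20% dropout. The dropout step is acceptable: 25/(1 − 0.15) = 29.4, rounded up to 30, and 5/30 = 16.7%. At 20%, division gives 31.25, rounded up to 32, while 25 × 1.2 = 30. The 25 itself cannot be reproduced, because no effect size, SD, test or sidedness is stated.

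**The possible within-person pairs.**

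| Pair | What the difference contains | Answers Objective 1? |
|---|---|---|
| 1 to 2 | Change over the 10 minutes, before UDS | No: UDS has not begun |
| 1 to 3 | Any benefit, plus the change from state anxiety to recalled peak, plus the effect of the test | No: three components mixed |
| 2 to 3 | As 1 to 3, starting after the exercise | No: same mixture |

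A rise during UDS is to be expected, since Section 5 describes the test as associated with anxiety.

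**What the shift does to a within-arm reading.** Let s be the rise from assessment 1 to 3 in controls and b the true benefit during UDS, in SD units with equal SDs at both assessments. Neither value is in the documents; I assume s = 0.5 to 1.0 and b = 0.5.

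- Control arm mean change: +s = +0.5 to +1.0.
- Mindfulness arm mean change: s − b = 0 to +0.5.
- Difference between arms: (s − b) − s = −b = −0.5, whatever s is.

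The mindfulness arm shows no reduction, while the between-arm difference recovers the whole benefit.

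**What the shift does to the paired test.** Suppose mindfulness has no effect and the third assessment exceeds the earlier one by a given number of SDs of the difference. Noncentral-t rejection rates at two-sided 0.05:

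| Shift | Paired, n = 25 | Paired, one arm, n = 12 | Between-arm test of change, 12 vs 13 |
|---|---|---|---|
| 0.25 | 22.5% | 12% | 5% |
| 0.5 | 67% | 35% | 5% |
| 1.0 | 99.8% | 88% | 5% |

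For positive shifts the paired rejections run towards a rise in anxiety and say nothing about mindfulness.

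**Precision of the between-arm options.** With score variance 1 and correlation r between assessments 1 and 3:

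- change score: 2(1 − r), which is 1.40 at r = 0.3 and 0.80 at r = 0.6;
- third score alone: 1.00;
- third score adjusted for the first: 1 − r², which is 0.91 and 0.64.

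The ratio of adjusted to change variance is (1 − r²)/[2(1 − r)] = (1 + r)/2, that is 0.65 and 0.80. The values of r are assumed.

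**What 25 subjects can detect** (two-sided 0.05, 80% power):

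- Paired, n = 25: 0.58 SD of the difference. Normal approximation: (1.960 + 0.842)/√25 = 0.56.
- Two arms, 12 vs 13: 1.17 SD. Normal approximation: 2.802 × √(2/12.5) = 1.12.
- Two arms, adjusted for assessment 1: roughly 1.17 × √(1 − r²), which is 1.12 at r = 0.3 and 0.94 at r = 0.6, ignoring the degree of freedom used by the covariate.
- If 25 meant 25 per arm: 0.81 SD. The documents do not support that reading, because total enrollment is 30.

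**The case against.** The best defence is that reduction may simply mean lower in the mindfulness arm than in the control arm. Section 7.4.2 uses the same word for physical distress measured by the pain VAS and UDS survey, for which no baseline is described, and Section 7.4.3 compares VAS scores between groups. The hypothesis also reads as a comparison with no mindfulness, and Section 6 places assessment after UDS, which fits the third form. This is a fair account of what the sponsor may have intended. It does not rescue the plan as written, because the only test named for anxiety is paired.

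Two stronger readings are tempting, and the documents do not support them.

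- A reader might infer that the mismatch of questions spoils any analysis using the third form, or that the data cannot answer Objective 1. Both arms complete the same three forms under 1:1 randomization, so a common shift cancels. Even a between-arm comparison of the 1-to-3 change would be unbiased. With the first score as covariate, analysing the third score or the change gives the same group effect, so differences involving the third form need not be prohibited.
- A reader might infer that the precision figures show harm from the peak question. They do not: (1 + r)/2 applies to any baseline and follow-up with equal SDs. It is a general argument for covariate adjustment, and at r = 0.6 the change score is less variable than the third score alone.

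Two further limits stand. The forms are not shown, so that assessments 1 and 2 record current anxiety is inferred from the term state anxiety and from the peak instruction being given only for the third. And Section 6 does not say that assessment is solely after UDS; it is merely out of step with Section 7.3.

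**Conclusion.** The concern holds for the within-person analysis that the plan specifies. The primary outcome names no assessment, the stated test is paired, and none of the three possible pairs measures a reduction of anxiety during UDS. This is more than missing detail, because following the stated rule can mislead: under an assumed shift of 0.5 to 1.0 SD, a real benefit of 0.5 SD would show as no change or as a rise.

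The pairing problem follows from the text, given the inference about the first two forms. The size rests on the assumed shift, benefit and correlation. The measurement schedule itself is adequate, since the third assessment compared between randomized arms addresses the hypothesis. The trial describes itself as a pilot, but it still states a hypothesis and a power target for a primary outcome, so the endpoint and contrast should be settled before the data are examined.

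**What to change.** - **Section 7.4.2:** name the third state-anxiety score (highest anxiety while undergoing UDS) as the primary outcome, compared between the mindfulness and control arms with the first score as covariate. Name the second score, compared between arms and adjusted for the first, as a secondary outcome for the immediate pre-UDS effect.
- **Section 7.4.3:** replace the paired t-test for anxiety with this ANCOVA, so that the two sections agree.
- **Section 7.4.1:** restate what 25 subjects can detect in a two-arm contrast: about 1.17 SD unadjusted for 12 versus 13 (two-sided 0.05, 80% power), smaller with adjustment by an amount that depends on the baseline correlation. State the effect, SD and sidedness assumed.
- **Section 6:** reconcile the sentence on questionnaires after UDS with the two pre-UDS assessments in Section 7.3.

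No new data are needed, since all three forms are already scheduled. The cost is that the pre-UDS change is no longer available as the primary result, and the sample-size basis looks less favourable. For example, a benefit of 0.5 SD of the outcome compared would have about 22% power in an unadjusted comparison of 12 versus 13. The sponsor would need to accept that for a pilot or revisit the sample size.

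### Enrolling 30 keeps the required 25 evaluable subjects only for losses up to 16.7%, not across the full 15-20% range stated in Section 7.4.1 (minor)

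*Combined protocol and SAP*

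**What the plan says.** Section 7.4.1 (Sample Size Estimation) says that "to achieve an alpha of 0.05 with power of 80" per cent, the "sample size should incorporate 25 subjects". It continues: "After accounting for 15-20% drop out/withdrawal, a total of 30 patients should" be enrolled. The table beneath has three relevant rows: a required sample size of 25, a row labelled "Estimate Participant Drop Out / Withdrawal" with the value 5, and a total enrolment of 30. Because the table adds 25 and 5 to reach 30, the 25 is a total over both arms and not a number per arm.

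Section 6 (Research Design) gives one number only: "A power calculation was performed and 30 subjects are required for this study". It mentions neither the 25 nor the allowance for loss.

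Section 7.3 says that randomization is "computer generated at a 1:1 ratio".

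**The concern.** A plan that states a range for dropout and says that enrolment accounts for it should still reach its evaluable target at the top of that range. Here the 20% end and the total of 30 do not fit together when the rate is applied to the subjects enrolled, which is the usual meaning of a dropout rate.

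What is at stake is the accuracy of the sample-size statement. The IRB and later readers would take it that the trial can lose one subject in five and still have the number on which its power rests. Section 6 adds a smaller difficulty: read alone, it suggests that the power calculation itself returned 30, when 7.4.1 says it returned 25.

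**Working it through.** **Inputs, all from Section 7.4.1**

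- Required evaluable subjects: 25 in total.
- Stated loss: 15% to 20%.
- Loss allowance in the table: 5 subjects.
- Total enrolment: 30.
- Alpha 0.05, power 80%. Effect size, standard deviation, sidedness and test are not stated.

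**Step 1. The plan's own total.** The table's sum is 25 + 5 = 30. Dividing the required number by the proportion retained also gives 30 at the low end of the range: 25/(1 - 0.15) = 29.4, rounded up to 30.

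**Step 2. The largest loss that 30 can absorb.** (30 - 25)/30 = 5/30 = 16.7%. This lies inside the stated range.

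**Step 3. Both ends of the range, and the limit.**

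| Loss | Expected evaluable of 30 | Enrolment needed for 25, as 25/(1 - loss) |
|---|---|---|
| 15% | 30 x 0.85 = 25.5 | 29.4, so 30 |
| 16.7% | 30 - 5 = 25 | 30 |
| 20% | 30 x 0.80 = 24 | 31.25, so 32 |

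Thirty is enough from 15% to 16.7%. Above 16.7% it is not, and at 20% the shortfall is 25 - 24 = 1 evaluable subject, or 32 - 30 = 2 enrolled.

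**Step 4. What one subject is worth.** The 25 cannot be reproduced without an effect size, so an assumption is needed: that 25 subjects give exactly 80% power at two-sided 0.05. The standardized effect is solved from that and then held fixed while the number falls to 24.

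- Two-sample t-test, 25 in total (12.5 per arm for the calculation): the implied effect is 1.17, and power with 12 per arm is 78.2%.
- Paired t-test, 25 pairs: the implied effect is 0.58, and power with 24 pairs is 78.2%.

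Either way the loss is 80.0 - 78.2 = 1.8 percentage points. The two effect sizes are products of the assumption and are not values the plan adopts.

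**Step 5. Section 6 against Section 7.4.1.** Section 7.4.1 separates the result of the calculation (25), the allowance (5) and the enrolment (30). Section 6 attaches the 30 to the power calculation. The enrolment figure is the same in both places; what differs is the description of what the calculation produced.

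**The case against.** The case for leaving the text alone is fair. The plan gives a range, and its table fixes one value inside that range, 5 of 30, and adds up correctly. The worst case is one subject and under two points of power, in a trial that Section 6 calls a pilot, and those points are measured from an 80% that cannot be verified. Under Section 7.3, consent, randomization and all questionnaires fall on the day of the procedure, so a 20% loss may be unlikely. Section 6 can be read as a summary of enrolment, since the table in 7.4.1 also describes 30 as an enrolment requirement. Deleting the range could also look like trimming an assumption to fit a number.

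Most of this bears on size and is accepted. It does not make the sentence right. The plan chose 20% as its upper end, offers no evidence for a lower figure, and allows for testing to be stopped (Section 9.1) and for withdrawal (Section 10.0). The worry about deleting the range is met by stating openly what a 20% loss would leave.

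A reader might be tempted to go further in three ways.

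- *That 30 fails the whole 15-20% range.* It does not; it holds from 15% to 16.7%.
- *That the sponsor multiplied by 1.20 where it should have divided by 0.80.* It is true that 25 x 1.20 = 30 and that 5 is 20% of 25. But division gives 30 as well, at 15% after rounding and at 16.7% exactly. The documents show no working, so the cause is unknown.
- *That a sizeable chance of ending below 25 shows a serious defect.* An allowance set on the expected loss always leaves some chance of falling short through ordinary variation, and this would remain with 32 enrolled. It says little about the discrepancy described here.

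**Conclusion.** The point holds as a minor error: the sentence in 7.4.1 is wrong as written for losses above 16.7%. At the 20% end, 24 evaluable subjects remain where 25 are required. This rests only on the plan's own figures and on reading the dropout rate as a share of those enrolled.

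The cost in power, about 1.8 points, is conditional on 25 giving exactly 80% with a two-sided t-test. A reader might conclude that the trial does not deliver 80% power. The documents do not support that as a flat statement: the basis of the 25 is not given, so power can be confirmed neither at 25 nor at 24, and at losses up to 16.7% the stated number is met.

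Section 6 is a wording mismatch with 7.4.1. A reader might infer from it that 30 evaluable subjects are needed and that no allowance for loss exists. The table in 7.4.1 rules that out, and no design or analysis decision turns on it.

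**What to change.** Enrol no additional patients. Make two changes of wording.

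1. In Section 7.4.1, replace the 15-20% range with an allowance of *up to 5 of 30 (about 17%)*, and add that *a 20% loss would leave 24 evaluable subjects, slightly below the 25 required for 80% power*. The 78% figure should not go into the protocol, because it is solved back from a sample size whose basis is not stated.
2. In Section 6, say that *25 evaluable subjects are required and 30 will be enrolled*.

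The cost is two edited sentences and a slightly less favourable stated tolerance for loss. Enrolment, design and analysis do not change.

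### The primary anxiety outcome is given only a paired t-test, which cannot compare the two independent randomised arms

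*Combined protocol and SAP*

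**What the plan says.** Section 6 sets out a parallel design: "Subjects will be randomized between standard clinic UDS or UDS with mindfulness exercises". Section 7.3 allocates 1:1 by computer. Neither section mentions matching or crossover.

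The Objective 1 hypothesis in section 3 is directional and tied to the intervention: "Hypothesis: anxiety will improve during UDS testing with prior mindfulness intervention". Section 7.4.2 states: "The primary outcome is a reduction in anxiety", measured by the anxiety survey. It names neither a time point nor a contrast.

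Under section 7.3 each subject gives three state-anxiety scores. The first comes after consent, in the exam room. The second follows the 10 minutes of quiet sitting or mindfulness. The third follows UDS and asks subjects to "assess their level of anxiety when it was at its highest while undergoing the UDS evaluation".

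Section 7.4.3 is the only text on analysis methods. For anxiety it says: "Paired t-test will be used to evaluate the anxiety difference". For pain it says: "ANOVA will be used to compare the visual analog scale scores between groups". A chi-squared test between the groups is assigned to the self-evaluation categories.

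Section 7.4.1 claims 80% power at alpha 0.05 and concludes that the "sample size should incorporate 25 subjects", with 30 enrolled to allow for dropout. It gives no test, effect size, SD or sidedness.

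**The concern.** A paired t-test needs pairs. With two unmatched arms, the only pairs are two scores from the same person, so the named test estimates change over time in whichever subjects are put into it. It does not estimate the difference between mindfulness and control, which is what randomisation was set up to provide.

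The sentence names neither arms nor time points. The authors may have meant a two-group comparison, since the sentences on either side of it are between-group. But the test they named cannot make that comparison.

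The risk is practical because the scores are not taken under like conditions. The first is a rating at rest before the procedure, and the third is a rating of peak anxiety during it. A change common to both arms is plausible for reasons unrelated to mindfulness. Such a change can make a paired test significant when mindfulness does nothing. If anxiety rises in controls and mindfulness prevents the rise, the paired test in the mindfulness arm has nothing to detect.

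**Working it through.** **1. Is there a between-arm test for anxiety anywhere?** Section 7.4.3 names three tests:
- ANOVA is limited to the visual analog scale scores.
- Chi-squared is limited to the self-evaluation categories, which 7.4.2 lists as secondary and the section 7.3 schedule lists separately from the anxiety questionnaire.
- The paired t-test is the only one attached to anxiety.

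No section gives a two-sample test, a comparison of change scores, ANCOVA or a repeated-measures model for anxiety. This step establishes the defect. The rest shows its possible size.

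**2. The plan's own figure.** The 25 in section 7.4.1 cannot be reproduced, because no effect size, SD, sidedness or test is stated. The dropout step roughly can: 25/(1 − 0.15) = 29.4, rounded up to 30, and 25/(1 − 0.20) = 31.25, rounded up to 32, against 30 stated.

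**3. Assumptions for the illustration.** 25 evaluable in total, 13 mindfulness and 12 control; two-sided alpha 0.05; changes in SD of the change score. The documents give no such changes, so a range is shown. Power comes from the noncentral t distribution:
- paired, n subjects: noncentrality d√n, n − 1 df
- two-sample: noncentrality d/√(1/n₁ + 1/n₂), n₁ + n₂ − 2 df

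**4. No mindfulness effect, same change in both arms (either direction).** For example, at 0.6 SD the noncentrality is 0.6√13 = 2.16 in the mindfulness arm and 0.6√25 = 3.00 if the arms are pooled.

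| Shared change | Paired, mindfulness arm (13) | Paired, control arm (12) | Mindfulness significant, control not | Paired, pooled (25) | Between-arm |
|---|---|---|---|---|---|
| 0 | 5% | 5% | 4.75% | 5% | 5% |
| 0.3 SD | 17% | 16% | 14% | 30% | 5% |
| 0.6 SD | 51% | 47% | 27% | 82% | 5% |
| 1.0 SD | 91% | 88% | 11% | 99.8% | 5% |

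The fourth column is the mindfulness-arm probability times (1 − the control-arm probability); at 0.6 SD, 0.512 × (1 − 0.475) = 0.269. A shared fall would read as benefit and a shared rise as harm.

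**5. A real effect.** Suppose controls rise by 1.17 SD and mindfulness fully prevents the rise.
- Between-arm test: significant in 80%.
- Paired, mindfulness arm: 5%.
- Paired, control arm: 96%.
- Paired, pooled: 66%, as a rise (by simulation).

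Control significant and mindfulness not occurs in 0.958 × 0.95 = 91%.

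**6. What 25 subjects can detect with 80% power.**
- Paired test on 25: 0.58 SD of change (0.584 × √25 = 2.92).
- Two-sample test of change, 12 vs 13: 1.17 SD (1.171/√(1/12 + 1/13) = 2.93), with 29% power at 0.58 SD.
- If 25 were per arm: 0.81 SD, with 53% power at 0.58 SD.

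**The case against.** The strongest reply accepts that a paired t-test cannot compare the arms and disputes how much follows.

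- **Intent.** The neighbouring sentences compare groups, so the anxiety sentence may be loose wording for a comparison of change scores. That may be so, but it is written nowhere, and such a comparison would be a two-sample test.
- **Objective 1 as worded.** Section 3 speaks of evaluating changes in anxiety, and a paired test does address change. This stands in part. What goes untested is the hypothesis that mindfulness produces the improvement.
- **Masking.** Read arm by arm, the control arm's rise would be significant in about 96% of trials in step 5, so the benefit would usually be visible. This stands: the benefit is hidden only if the control arm is ignored or the arms are pooled. But setting one significant result beside one non-significant result is not a test of the difference, and step 4 shows that pattern arising in up to 27% of trials with no effect.
- **Pooling.** Nothing in the plan proposes pooling the arms, so the largest percentages rest on a less likely reading. Fair; the arm-by-arm columns matter more.
- **Total or per arm.** Section 13.0 projects 6 patients a month for 10 months, which is 60, not 30. Sections 6 and 7.4.1 point to 30 in total, so 12 vs 13 is the better reading, but the power figures depend on it.
- **Pilot status.** Section 6 calls the trial a pilot, which tempers the consequence. The plan still claims 80% power and randomises a control group, which it should use.

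**Conclusion.** The concern holds, and the primary analysis must be corrected. The only test named for the primary outcome cannot compare the randomised arms, and no other text fills the gap. This is an error in the stated method, not a missing detail, and it depends on no assumed number.

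The paired-test error is confined to anxiety: the pain VAS and the self-evaluation categories have between-group tests. The UDS survey, also a secondary outcome in 7.4.2, has no test named in 7.4.3, which is a separate gap.

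Under the assumed shared changes of 0.3 to 1.0 SD, a mindfulness-arm paired test would be significant in 17% to 91% of trials with no mindfulness effect, against a nominal 5%. These figures rest on 13 and 12 evaluable subjects, two-sided alpha 0.05 and shared changes the documents do not give. The comparison of 0.58 with 1.17 SD shows what the choice of test does to the power claim. It does not prove that 25 is wrong, since 7.4.1 does not state what the 25 was calculated for.

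**What to change.** **Section 7.4.3.** Replace the anxiety sentence with a between-arm comparison. A two-sample t-test of change from the initial score is enough. Preferred wording:

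> The primary analysis compares the randomised arms on the third (during-UDS) state-anxiety score by ANCOVA, with arm as factor and the initial state-anxiety score as covariate. The adjusted between-arm difference with its 95% confidence interval is the primary result. Paired t-tests within each arm are descriptive only.

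**Section 7.4.2.** State the primary time point. The third score is suggested because Objective 1 concerns anxiety during UDS, but the authors must confirm it.

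**Section 7.4.1.** Restate the sample size for the between-arm test, with effect size, SD and sidedness. Say whether 25 is the total or per arm, and reconcile this with the accrual projection in section 13.0.

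**Cost.** Wording only; the scores are already collected under section 7.3. The restated power may show that 25 subjects in total detect only a large effect. For 12 vs 13 and 80% power, in SD of the raw score and with assumed baseline correlations:

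| Correlation | Third score alone | Change score | ANCOVA |
|---|---|---|---|
| 0 | 1.17 | – | 1.20 |
| 0.5 | 1.17 | 1.17 | 1.04 |
| 0.7 | 1.17 | 0.91 | 0.86 |

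The change-score column is 1.171 × √(2(1 − ρ)). The ANCOVA column uses 22 df and residual variance scaled by 1 − ρ², and allows for chance baseline imbalance by averaging over simulated baselines.
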